#### Family caregiver

- 1. age 18 and above
- 2. are related to the patient by blood, marriage, adoption, or affinity as a significant other (defined by the legally authorized person as the primary person providing oversight and support on an ongoing basis)
- 3. speak English or Spanish
- 4. able to recall at least two words on the Three Word Recall
- 5. participate, at a minimum, in the initial assessment and development of FamPath

**Nurses** (at the conclusion of the intervention at each site)

- 1. identify the intervention unit as the primary unit worked
- 2. speak English or Spanish

FOR THE EXPLORATORY AIM of assessing the cultural appropriateness of the intervention, we will recruit *family CGs* who self-identify as black, Latino, Asian and white, randomly selected from the Fam-FFC sample. Approximately 10 percent of families from each ethnic group represented in the study will be approached for consent for participation in interviews. (If theoretical saturation is not reached, interviews will continue until saturation is reached). Additionally, the *six nurse champions* will be consented and interviewed after the study ends in his/her particular unit/setting to provide their perspective on the cultural appropriateness of Fam-FFC.

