#### For both patient and family caregiver:

- 1. Subject consent withdrawal
- 2. Death
- 3. Failure of subject to adhere to protocol

The Intent-To-Treat Principle will be followed to analyze data from the current proposed trial.

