#### SITE Procedures (These procedures are repeated for Sites 1, 2 and 3.)

**Pre-intervention**: Baseline setting (census, ownership, etc.) as well as an environmental and policy information will be collected by the research evaluator on the two study units. The units will be randomized into treatment or control arm. Nurse champions (two per the intervention unit) will be recruited and consented.

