#### 7.4.5 Blinding of the Test Article

Describe how the test article is blinded.

To ensure comparable samples in both the treatment and control condition participants will be blinded to treatment arm prior to consent, since the Fam-FFC treatment requires more effort that the control condition.

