#### 8.3 Statistical methods

Describe the statistical methods (or non-statistical methods of analysis) that will be employed.

Aim 1: Validate the efficacy of Fam-FFC on physical function (ADLs/ performance and physical activity), delirium occurrence and severity, behavior, and mood. For each outcome, an appropriate mixed effects model (either a LME or a GLMM) will be identified for model fitting. For delirium occurrence (a binary variable) we will use generalized linear mixed models with a logistic link function. The primary independent variables will be GROUP (Fam FCC v. control), TIME (day of admission, day of discharge, 2-month post discharge and 6-month post discharge) and SITE (for the three hospitals). The TIME x GROUP interaction will be tested for differential rate of change in the outcome. The GROUP x SITE interaction will be tested for heterogeneous center effects. Three-level models using an unstructured correlation will be fitted for the repeated measures within individuals who are nested within the same inpatient unit. 181-184 Time will be modeled continuously using day since admission so that trajectories can vary across individuals depending on time spent in the inpatient unit. This also allows us to examine non-linear time functions (e.g., quadratic) that allow the rate of change to vary over the different intervals. Covariates identified from the baseline analyses will be included in the mixed model to adjust for their influences. We will also consider interactive effects among demographic variables of interest (e.g., age, gender of patient and caregiver, ethnicity) and treatment condition to identify moderators of the treatment effects. Bootstrap methods will be applied to the mixed effects models in addition to the Wald test and the likelihood ratio test within the mixed effects models. 185-187 Subject level propensity score matching will be applied to improve the statistical power of the planned hypothesis tests.  To address the multiple endpoints issue in this trial, P<0.05 for the primary hypothesis and then multiple testing procedures such as closed testing implemented in PROC MULTTEST will be applied to adjust p values. 188-190

Aim 2: Evaluate the impact of Fam-FFC on family CG-centered outcomes (family CG preparedness for caregiving, strain, burden, and desire to institutionalize). LME similar to Aim 1, will be used.

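### Propensity-score matching is justified only by power, no gain over a covariate-adjusted full-sample model is shown, and the plan does not say whether the matched or the full-sample result is the test

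*Combined protocol and SAP*

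**What the plan says.** For Aim 1, section 8.3 plans a three-level mixed model (repeated measures, patients, inpatient units). On adjustment: "Covariates identified from the baseline analyses will be included in the mixed model to adjust for their influences". On the treatment comparison: "The TIME x GROUP interaction will be tested for differential rate of change in the outcome". Wald, likelihood ratio and bootstrap tests are all listed. Then: "Subject level propensity score matching will be applied to improve the statistical power of the planned hypothesis tests". That sentence cites reference 175, whose title in section 22.0 concerns propensity scores in cluster randomised trials with selection bias. For Aim 2: "LME similar to Aim 1, will be used".

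The plan gives no propensity model, matching ratio, caliper or rule for unmatched patients. It does not say whether the subject being scored is the patient, the caregiver or the dyad. The power statement in section 8.2 does not mention matching.

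Three other places bear on the point:

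- Section 3.3.1: "The Intent-To-Treat Principle will be followed to analyze data from the current proposed trial".
- Section 7.2, before recruitment starts: "The units will be randomized into treatment or control arm".
- Section 7.4.5: "To ensure comparable samples in both the treatment and control condition participants will be blinded to treatment arm prior to consent".

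**The concern.** Two analyses of the same hypothesis are planned, one on all patients with covariate adjustment and one on matched subjects, and neither is named as the test. They can give different estimates and p-values. The multiplicity procedure in section 8.3 deals with several endpoints; it does not cover a choice between estimators. Whoever runs the analysis could report either result as the planned one.

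The stated benefit is also doubtful. Matching adds no patients and no units. When the outcome model already uses the covariates, the usual effect of 1:1 caliper matching is to discard information.

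A propensity method could have a sound purpose here. Units are randomised before patients are recruited, so the arms can differ through who is approached or agrees. Section 3.1 also requires caregivers to "participate, at a minimum, in the initial assessment and development of FamPath", although section 7.2 delivers FamPath only on intervention units. The sentence in 8.3 does not give the method that purpose.

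**Working it through.** **1. The plan's own figures.** 6 units × 73 = 438. With 20% attrition, 438 × 0.8 = 350.4, or 175.2 per arm and 58.4 per unit. The 80% power cannot be reproduced, because section 8.2 gives neither an effect size nor an ICC. Back-solving without clustering, two-sided 5%: 2 × (1.960 + 0.842)² / 0.30² gives 175 per arm; 175 / 0.8 gives 219; total 438. With an effect of 0.5 SD, 438 would fit an ICC of about 0.031. Both are assumptions. No figure is stated for a gain from matching.

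**2. Matching that keeps everyone.** The same patients and covariates then enter the adjusted model, so there is nothing to gain by information. Propensity weighting of all patients plus covariates, simulated for a single outcome, was at most 1.4 points below the adjusted model and never above it. One exception: keep-all pairs with a paired t-test in place of covariates beat the adjusted model by about 0.5 to 2 points when the covariates explained nothing (R² = 0), because useless covariates were left out. At R² = 0.5 it had 81.3% power against 97.4%.

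**3. Matching that drops patients, with clustering.** Take 3 units per arm, m = 58.4 patients per unit, a fraction k kept, and V = ICC + (1 − ICC)/m, with m replaced by k × 58.4 after matching. Set the effect to give 80% full-sample power at each ICC. Power after matching = Φ(2.802 × √(V_full / V_matched) − 1.960).

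Example, ICC 0.02 and k = 0.845: V_full = 0.02 + 0.98/58.4 = 0.03678. V_matched = 0.02 + 0.98/49.35 = 0.03986. Root of the ratio = 0.9606. Φ(0.731) = 76.8%, a loss of 3.2 points.

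| ICC | 84.5% kept: power (loss) | 78% kept: power (loss) |
|---|---|---|
| 0 | 73.1 (6.9) | 69.6 (10.4) |
| 0.01 | 75.6 (4.4) | 73.3 (6.7) |
| 0.02 | 76.8 (3.2) | 75.1 (4.9) |
| 0.05 | 78.2 (1.8) | 77.3 (2.7) |
| 0.10 | 79.0 (1.0) | 78.5 (1.5) |

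The fractions kept come from simulating 1:1 matching with a caliper of 0.2 SD of the logit and 8 covariates: 84.5% with no imbalance, and 78% with arm imbalance of SD 0.15 per covariate. Clustering shrinks the loss because dropping patients leaves the between-unit variance unchanged.

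**4. Single outcome, no clustering, both analyses adjusted** (5,000 simulated trials, 175 per arm, effect 0.3003 SD). Full sample against matched, at R² = 0, 0.25 and 0.5:

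- No imbalance: 79.0/72.9, 88.7/84.2, 97.4/95.2.
- With imbalance: 77.4/69.8, 87.6/81.2, 96.7/93.3.

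The loss is about 2 to 8 points in every setting.

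**5. The TIME × GROUP test.** Covariate main effects cancel out of a within-patient slope, so a model with main effects only is not effectively adjusted for this test. The table gives power (%) for per-patient slopes, no clustering, where covariates explain a share R² of the slope. The last row of each block is the full-sample adjusted result from step 4. It applies because a slope is one outcome per patient, with the same effect, sample size and R².

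| | R² 0 | 0.25 | 0.5 |
|---|---|---|---|
| **No imbalance** | | | |
| Full sample, main effects only | 80.2 | 80.4 | 80.5 |
| Caliper-matched | 72.4 | 76.0 | 80.8 |
| All patients weighted | 79.6 | 82.0 | 89.1 |
| Full sample, slope adjusted | 79.0 | 88.7 | 97.4 |
| **Imbalance SD 0.15** | | | |
| Full sample, main effects only | 79.5 | 75.0 | 73.1 |
| Caliper-matched | 71.6 | 70.8 | 74.0 |
| All patients weighted | 77.2 | 78.4 | 84.2 |
| Full sample, slope adjusted | 77.4 | 87.6 | 96.7 |

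A further run at R² 0.5 with imbalance gave 70.7% full sample and 75.0% matched. So matching can gain on the main-effects-only model, but it stays well below adjusting the slope directly. With imbalance, the main-effects-only slope test also had a type I error of 10.0% (R² 0.25) and 16.6% (R² 0.5); the matched test had 2.0% and 1.2%.

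**The case against.** The strongest defence is that matching can help the very test section 8.3 names. If covariates enter as main effects only and they predict the slope, a matched or weighted analysis can gain power and protect the type I error. That stands, and it rules out the stronger reading that matching cannot add power. It does not rescue the rationale, because adding covariate × TIME terms to the full-sample model does better.

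Second, the losses are assumed and clustering makes them small. This also stands. The background section calls the pilot effects moderate. With an effect of 0.5 SD and an ICC near 0.031, the loss is roughly 2 to 5 points. A smaller loss is still not a gain.

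Third, reference 175 suggests the authors had selection bias in mind, and the plan takes care over selection: recruitment procedures are the same on both units, evaluators are not told the allocation, and participants are blinded before consent. A reader should therefore not infer that selection was ignored. What remains is that the stated purpose does not match the title of the cited source. A score built on measured covariates may also not repair the caregiver criterion that refers to FamPath.

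Fourth, the matched analysis may be only supportive. A reader might infer a breach of intention to treat, but the documents do not say that unmatched patients are dropped from the main test. The conflict arises only if they are.

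**Conclusion.** The concern holds in this form: the power rationale is unsupported, and the role of matching is undefined. Against an effectively adjusted full-sample model, 1:1 caliper matching costs about 2 to 5 points at ICC 0.02 to 0.05 with 78% to 85% of pairs kept, and up to about 6 to 10 points without clustering. The effect size, ICC, R², imbalance, caliper, number of covariates and visit days are all assumptions, so these figures illustrate direction and rough size only. The clustered figures use a normal approximation and make no allowance for having only six units.

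The textual gap rests on no assumption: nothing says which result is tested at P<0.05, which of the three listed tests decides, or who is matched. That permits a choice after both results are seen. It does not show that one is intended.

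**What to change.** In section 8.3, delete the clause giving power as the purpose of matching. Suggested text:

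*The planned hypothesis tests use the covariate-adjusted mixed model on all enrolled dyads, analysed by allocated unit. The prespecified baseline covariates enter as main effects and as covariate × TIME terms. The decisive test is [one of Wald, likelihood ratio or bootstrap].*

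The sponsor should list the covariates, for patient and for caregiver outcomes, before unblinded data are seen; no particular list is required. If pre-admission Barthel is among them, say how it is used, because it is also the reference for return to baseline.

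If a propensity method is kept, make it one prespecified sensitivity analysis for selection at recruitment. It should retain all patients (weighting or full matching), use only variables that exposure to the unit cannot change, and state whether it scores the patient or the dyad.

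Cost: SAP wording and a few more model terms, with no new data. A matched result could no longer be presented as the main test.

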## 1.0 Objectives

#### 1.1 Study Objectives

Describe the purpose, specific aims or objectives. State the hypotheses to be tested. Describe the treatment that is considered standard of care (i.e., indicate how patients would be treated in a non-investigational setting). Indicate if the study test article(s) is available to patients without taking part in the study.

The overall aim of this study is to conduct a formal, real world test of the efficacy of Family-centered function-focused care (Fam-FFC) on patient and caregiver-centered outcomes in community-dwelling, hospitalized older adults with very mild to moderate dementia.

Aim 1: Validate the efficacy of Fam-FFC on physical function (ADLs/ performance and physical activity), delirium occurrence and severity, behavior, and mood.

**H1**: Patients exposed to Fam-FFC will demonstrate more return to baseline ADL function as compared to those in the control condition.

**H2:** Patients exposed to Fam-FFC will demonstrate increased physical activity, improved chair rise and less delirium occurrence and severity, less NPS, and less depression, as compared to those in the control condition.

Aim 2: Evaluate the impact of Fam-FFC on CG –centered outcomes.

**H3:** CGs exposed to Fam-FFC will demonstrate improved preparedness for caregiving, and less strain, burden, and desire to institutionalize as compared to those in the control condition.

Aim 3: Evaluate the relative costs for Fam-FFC v. control condition, and calculate health care (post-acute health care utilization) costs and total cost savings for Fam-FFC.

 $H_4$ : Patients exposed to Fam-FFC will demonstrate higher intervention costs but lower post-discharge cost for health care services (emergency room admissions, hospital admissions, and long-term nursing home admissions) as compared to those in the control condition.

**H**5: Patients exposed to Fam-FFC will demonstrate total cost savings overtime as compared to those in the control condition.

Exploratory Aim: Assess the cultural appropriateness of Fam-FCC for diverse families.

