Aim 3: Evaluate the relative costs for Fam-FFC v. control condition, and calculate health care and total cost savings for Fam-FFC. Standard micro-costing methods will be used to estimate costs. Using the guidelines offered by Chatterji and colleagues, 191 total intervention costs will be based on expenditures/outlays for each of the following: (1) intervention; (2) consultant fees; (3) personnel costs, (4) incentives, meals, travel for study participants; (5) utilities, maintenance, security and other operating costs; and (6) administrative costs. We will identify all of the "inputs" that go into the implementation and then assign unit costs to these inputs (wages/salaries acquired from the unit managers, cost of materials, etc.). Then, we will multiply the units of inputs by their unit costs and sum this across all of inputs to determine the total cost of implementation per setting. An average across all settings will then be calculated. To estimate the cost of healthcare for each group, we will collect unit costs from existing literature including data published yearly by the American Medical Association, the American Hospital Association, the National Hospital Discharge Survey, and the American Managed Behavioral Healthcare Association. Similarly, these unit cost estimates for each type of health care utilization (emergency room, hospital and long-term nursing home admissions) will then be multiplied by the number of units used by each individual in the sample. A variable will be created for total health care cost by summing across conditions while exercising care to avoid any double counting of services. Health care and total cost savings will be calculated for each treatment condition. Mean costs and savings will be computed and subsequently tested for statistical significances across conditions using a t-test. In calculating cost we will also take into account fixed versus variable costs adjusting for variation over time in wages, benefits, and supplies using a standard micro-costing approach. We will then use multivariable regressions to determine whether Fam-FCC is significantly related to lower costs of healthcare and total cost savings controlling for covariates. Moreover, we will compare health care costs in terms of changes over time with paired t-test (within group differences) and with parametric Analysis of Variance (between group differences).

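### Aim 3 plans three between-arm tests of health care cost and two of total cost savings, and names none of them as deciding H4 or H5

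*Combined protocol and SAP*

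**What the plan says.** Section 8.3, Aim 3, describes three between-arm significance tests in sequence.

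- **t-test.** "Mean costs and savings will be computed and subsequently tested for statistical significances across conditions using a t-test". It covers health care cost and total savings, with no adjustment.
- **Regression.** "We will then use multivariable regressions to determine whether Fam-FCC is significantly related to lower costs of healthcare and total cost savings", controlling for covariates. It covers the same two outcomes. No covariates are listed for Aim 3.
- **ANOVA.** Change in health care cost over time is compared within groups by paired t-test and between groups "with parametric Analysis of Variance (between group differences"). Total cost savings are not named here.

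The hypotheses are in section 1.1. H4 expects intervention costs to be higher with Fam-FFC and predicts "lower post-discharge cost for health care services". H5 reads: "Patients exposed to Fam-FFC will demonstrate total cost savings overtime as compared to those in the control condition". Neither is tied to a test, there or elsewhere. Section 1.2 lists relative costs, health care cost and total cost savings among the primary endpoints.

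The only significance level and multiplicity rule stand in the Aim 1 paragraph of 8.3: "To address the multiple endpoints issue in this trial", the plan applies "P<0.05 for the primary hypothesis and then multiple testing procedures such as closed testing implemented in PROC MULTTEST". No level, sidedness or rule for conflicting results is given for Aim 3.

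**The concern.** With several tests of one outcome and none designated, the analyst can choose after seeing the results which p-value speaks for H4 or H5. The tests can also disagree, and the plan does not say what follows if they do.

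The ANOVA adds a further problem because it does not estimate what the other two estimate. The t-test and regression compare costs over the follow-up; the ANOVA compares how cost moves between periods. The cost outcomes paragraph in section 7.2 describes utilization to six months after discharge and no pre-admission cost baseline. Change can therefore only mean one post-discharge period against another. An arm with high early and lower later cost would do well on change while costing the same in total.

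At stake is a cost claim that the plan ranks as primary.

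**Working it through.** The documents state no error rate for Aim 3, so there is no figure of the plan's own to reproduce. The check asks how often at least one test is significant when the arms do not differ.

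**Inputs from the documents.** Level 0.05 (8.3, Aim 1 paragraph). Three between-arm tests for health care cost and two for total savings (8.3, Aim 3). 438 dyads and 20% attrition (8.2): 438 × 0.8 = 350.4, or 175 per arm.

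**Assumed inputs.** Each test is two-sided at 0.05, and any one significant result counts. Covariate R² is 0.05 to 0.5. The correlation of total with change, r, is 0 to 0.9. Patients are independent (no clustering).

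**Reference values if tests were independent.** Two tests: 1 − 0.95² = 0.0975. Three tests: 1 − 0.95³ = 0.1426.

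**Correlated tests.** The correlation of the t-test with the regression is √(1 − R²), that of the t-test with the ANOVA of change is r, and that of the regression with the ANOVA is r√(1 − R²). Simulating the three z-statistics (2,000,000 draws per setting) gives the chance of at least one significant result:

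| R² | √(1 − R²) | t-test and regression | all three, r = 0 | all three, r = 0.5 | all three, r = 0.9 |
|---|---|---|---|---|---|
| 0.05 | 0.975 | 0.060 | 0.107 | 0.100 | 0.079 |
| 0.10 | 0.949 | 0.065 | 0.111 | 0.104 | 0.082 |
| 0.20 | 0.894 | 0.071 | 0.118 | 0.110 | 0.088 |
| 0.50 | 0.707 | 0.083 | 0.129 | 0.122 | 0.101 |

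- Health care cost, three tests: 0.079 to 0.129, which is 1.6 to 2.6 times 0.05.
- Total savings, two tests: 0.060 to 0.083, which is 1.2 to 1.7 times 0.05.
- Health care cost, favourable direction only: 0.040 to 0.066 against 0.025.

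**Where the excess comes from.** At R² = 0.2 and r = 0, adding the ANOVA moves the rate from 0.071 to 0.118. The t-test and regression nearly duplicate each other; the change test does not.

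**Which r is plausible.** With two follow-up periods of variance v₁ and v₂ and between-period correlation ρ, r = (v₂ − v₁)/√[(v₁ + v₂)² − 4ρ²v₁v₂]. Equal variances give r = 0. Data are collected at 2 and 6 months, so the periods last about 2 and 4 months and the variances may well differ. For v₂/v₁ = 2 and ρ = 0, r = 1/3 = 0.33. For v₂/v₁ = 4 and ρ = 0.6, r = 3/√(25 − 5.76) = 0.68. Hence the wide range for r.

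**Patient-level check.** 175 per arm, two periods, R² 0.1 to 0.3, ρ = 0.3, SD ratio 1 to 3, normal or log-normal costs, 10,000 runs per setting. Each test alone held 0.047 to 0.053. At least one of the first two was significant in 0.068 to 0.078 of runs, and at least one of three in 0.095 to 0.126.

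**Clustering, kept separate.** Six units are randomized, and the t-test and ANOVA as described carry no term for them. In the same simulation (R² = 0.2, ρ = 0.3, equal variances), a unit effect shared by both periods with an ICC of 0.01 in each period raised the t-test alone to about 0.15. Because the effect is shared, the ICC of the total is higher: the patient-level variance of the total is 4 × 0.2 + 0.8 × 2.6 = 2.88, so the ICC is 0.04/(0.04 + 0.99 × 2.88) = 0.014.

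**The case against.** The strongest reply is that the Aim 3 text implies an order. The t-test comes first and is descriptive in tone; the regression is introduced in hypothesis language, "multivariable regressions to determine whether Fam-FCC is significantly related to lower costs of healthcare and total cost savings controlling for covariates"; and the change analysis is appended as an extra. On that reading the regression is the main analysis. It is a natural reading, but it stays an inference: the t-test is also described as a significance test, nothing is labelled supportive, and the regression's covariates are open.

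A second reply is that closed testing already controls error. It does not settle this point. The sentence is about endpoints, offers closed testing only as an example, and does not identify the primary hypothesis. Even with a fixed alpha for H4, one would not know which of three p-values to set against it.

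Three stronger readings are tempting, and the documents do not support them.

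- *The error rate doubles for both H4 and H5.* The ANOVA is confined to health care costs, so H5 has two highly correlated tests and the excess is one to three percentage points.
- *The doubling follows from the plan.* It does not. Every figure depends on assumed correlations, and change over time is itself undefined.
- *The plan will claim savings on any one significant result.* No passage says so; the plan merely fails to exclude it. Moreover, H4 and H5 are directional, so the two-sided rates include false findings that Fam-FFC costs more.

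**Conclusion.** The point holds for the missing decision rule and, with bounds, for its size. Health care cost has three between-arm tests and total savings has two; none decides, and the multiplicity sentence does not cover alternative analyses of one outcome.

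Under the stated assumptions the false-positive chance is roughly 8–13% for H4 and 6–8% for H5, with about 4–7% against 2.5% for a favourable H4 result. The H4 excess comes mostly from the ANOVA of change, which answers a different question from total cost.

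A reader might infer that naming one test restores 5%. It removes this multiplicity only. The chosen model must also account for the randomized units, since clustering can inflate a single test by more than the choice among tests does.

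**What to change.** In 8.3, Aim 3, add:

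> The post-discharge cost part of H4 is decided by the covariate-adjusted between-arm difference in mean total health care cost over six months, from the multivariable regression with covariates fixed in advance and with the randomized inpatient unit accounted for. H5 is decided by the same model for total (intervention plus health care) cost. The intervention-cost part of H4 is reported descriptively from the per-setting micro-costing. The t-test and the ANOVA of change are supportive, reported as estimates with 95% CIs, and cannot establish H4 or H5.

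One limit should be stated beside it. The plan computes intervention cost per setting and averages it across settings, so in the H5 model it enters as close to a constant per arm. The H5 interval will then mainly reflect variation in health care cost.

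The change needs no new data or patients. The price is that a significant t-test or ANOVA can no longer carry the cost claim alone, and that accounting for six units will widen the intervals.
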